10.5 Patient Disposition

An overview table will be provided for all patients and will include the number of patients enrolled, the number of patients in each analysis population set, the number of completers and the number of withdrawals and the reasons for withdrawal. Compliance parameters for drug administration will be tabulated.

Demographic information will be summarised using descriptive statistics or counts and percentages.

General medical histories and DLBCL-specific- medical histories will be summarised by counts and percentages using appropriate classification codes. Concomitant medications will be recorded and tabulated with counts/percentages showing the number of medications/percentage used in each medication class.

10.6 Analysis of Efficacy Data

10.6.1 Primary Efficacy Endpoint ORR

Local and independent response evaluations (progressive disease, SD, PR and CR) will be tabulated with counts/percentages for each visit available. Missing response evaluations will be taken into account, with patients with missing responses included in the denominator for calculating the rates).

Objective response is defined as being when a patient is classified as having a CR or PR after DLBCL evaluation using the IWG treatment response criteria for malignant lymphoma ([Cheson et al., 2007](#); see [Appendix G](#)).

The ORR, for the primary efficacy endpoint, is defined as the proportion of patients with a CR or PR (ORR = CR + PR) up until disease progression, based on central radiological + clinical evaluations.

The denominator for calculating the rate will be based upon the total number of patients in the FAS population. As a sensitivity analysis, patients without any post-baseline assessment of response will be included in the denominator for ORR calculation. The number of responding patients and respective rates as well as the 95% confidence limits will be presented.

The SAP will specify further sensitivity and supportive analyses, as well as possible evaluation of further response parameters (e.g., best response).

10.6.2 Secondary Endpoints

10.6.2.1 Disease Control Rate (DCR)

The DCR is defined as CR + PR + SD (i.e. ORR + SD) and will be evaluated as for ORR.

10.6.2.2 Duration of Response (DoR) and Time to Next Treatment (TTNT)

DoR is defined as the time interval between the initial time point of tumour response (CR or PR whichever status is recorded first) and the first date that recurrence of progressive disease is documented. Response duration by the local and central assessment will be tabulated with descriptive statistics.

Disease progression is defined as the first occurrence of progressive disease according to the revised response criteria ([Cheson et al., 2007](#)) as assessed by central radiology / clinical readers.

TTNT is defined as the time from study entry (= first dosing) to the institution of next therapy for any reason including disease progression, treatment toxicity and patient preference. TTNT will be descriptively analysed.

10.6.2.3 Time to Event Variables: Progression-Free Survival (PFS), Overall Survival (OS), and Time to Progression (TTP)

PFS is defined as the time elapsed between study entry (= first dosing) and lymphoma progression or death from any cause, whichever occurs first. Patients not experiencing a lymphoma progression or death from any cause will be censored at the last available tumour assessment. The same holds true for patients who are lost-to-follow-up.

OS is defined as time from study entry (= first dosing) until the date of death from any cause. Patients who are alive but have dropped out early will be censored at the time of the last available study visit assessment.

TTP is defined as the time from study entry (= first dosing) until documented lymphoma progression or death as a result of lymphoma. The events of interest are only disease progression and death from lymphoma. Death from other causes will not be taken into account (will be censored) in the TTP evaluation. Patients not experiencing progressive disease will be censored at the last NHL assessment. Deaths from other causes will be censored at the time of death. Early drop-outs without any documented date of progression will be censored at the time of the last NHL assessment.

Kaplan-Meier methodology will be used to evaluate median survival, presenting corresponding statistical parameters and Kaplan-Meier survival curves. Further analyses concerning influence of IPI and GC/non-GC B-cells will be specified in the SAP.

TTP will be compared to the TTP of the patients' most recent therapy by tabulating descriptive statistics (including 95% confidence limits).

For the purposes of the protocol the day of enrolment is defined as the date of the first treatment (study entry).

The SAP will provide further details on how to evaluate the influence of IPI and GC/non-GC B-cells on ORR, DCR, PFS, OS, DoR, TTP and TTNT. Analyses will apply Kaplan-Meier methods using these parameters as factors, as well as stratifying analyses results by these factors or including these factors in appropriate multivariate models (e.g., analysis of variance [ANOVA]).

The analysis of incidence and severity of AEs has been described below.

10.6.2.4 Immunogenicity Analysis

The absolute number and percentage of patients, who develop anti-MOR00208 antibodies, and the results of semi-quantitative anti-MOR00208 antibody titre determinations of confirmed positive sample assessments will be tabulated. Further details will be specified in the SAP.

10.6.2.5 Pharmacokinetic Analysis

Appropriate PK parameters for MOR00208, with a focus on, but not limited to, accumulation ratios, will be computed based on non-compartmental data analysis and summarised using descriptive statistics. Mean concentrations (on original and on log-linear scale) will be visualised in figures. Further details of the PK analysis will be specified in the SAP.

10.6.2.6 Biomarkers

Blood and protein biomarkers which are important in the mechanism of action of, or could predict response to, the study drugs will be descriptively tabulated, presenting absolute and change to baseline values, if applicable.

For example:

- a. Fc γ RIIa and Fc γ RIIIa genotyping results will be descriptively tabulated, whereas ORR and selective AEs tabulations will be split by these factors

b. Flow cytometry results of CD16 expression on NK cells will be descriptively tabulated, as well as ADCC results.

10.7 Analysis of Safety Data

10.7.1 Adverse Events

MedDRA (version 18.0 or higher) coded AEs will be used to show the incidence of all AEs by SOC, PT, relationship to treatment, severity and seriousness.

An AE summary table will present the number of events, number of patients and the percentage of patients having TEAEs, SAEs, and TEAEs that led to study discontinuation.

AE frequency tables will display event and patient counts by MedDRA, SOC and PT for each treatment arm. Such summaries will be displayed for all TEAEs, TEAEs by maximum severity/toxicity, TEAEs by relationship to study drug, SAEs, drug-related TEAEs and TEAEs that led to study discontinuation.

10.7.2 Clinical Laboratory Evaluations

The analysis of laboratory parameters for each treatment arm will be presented separated into blood parameters (e.g., haematology, serum chemistry, coagulation, serology for hepatitis B and C) urine parameters (e.g., urinalysis) and serum pregnancy test.

Descriptive summaries of actual (absolute) values and selected change-from-baseline values for continuous laboratory parameters of interest will be presented. Investigator assessments of the clinical relevance of each laboratory parameter will be analysed by frequency tabulations.

The assessment of categorical urinalysis variables will be tabulated by time point, results for example of hepatitis B and C serology and pregnancy test results will be summarised using counts/percentages. Further details (e.g., tabulation of shifts, special analyses with respect to NCI CTC grading) will be detailed in the SAP.

10.7.3 Physical Examination, Vital Signs and Electrocardiogram (12-lead ECG)

Complete and limited PE results will be summarised by body system and tabulated as counts/percentages. New and worsening abnormal physical examination findings during the study will be entered as AEs and analysed within the AE tables in detail. Descriptive summaries of vital sign parameters will be calculated. Summary ECG assessments will be tabulated by time point using frequency tabulations. Results of the 12-lead ECG (PR, QRS, QT, RR interval values) will be flagged to show whether a value is below or above the normal limit and summary statistics will be provided for ECG parameters.

10.8 Sample Size Determination

Approximately 80 patients with R-R DLBCL who meet the inclusion criteria and have none of the exclusion criteria will be randomly enrolled into the study. The study will be performed with an interim stop for the evaluation of the safety of the LEN dosage. No adjustment of sample size

or adaptation of efficacy evaluations will be made at this point. As the primary purpose of this study is to evaluate the clinical efficacy of 25 mg daily oral LEN combined with 12 mg/kg MOR00208 administered by IV infusion in patients with R-R DLBCL, no formal statistical hypothesis testing will be performed.

For the determination of a suitable sample size, it is assumed that the combination treatment could improve the ORR from a value of 20% (under monotherapy) to 35% (under combination therapy). Applying an exact binomial test with a two-sided significance level of 5% and a power of 85% the estimated sample size is 73 patients (calculation performed by nQuery Advisor® 7.0). According to this scenario an observed ORR of 32% would lead to a statistically significant study outcome. Assuming a drop-out rate of 10%, a total sample size of about 80 patients is estimated.

The sample size determination has been conducted using various possible monotherapy and combination effect ORR rates and various power assumptions. Literature evaluation of study results concerning the ORR rates of LEN or comparable products (as mono- or combination-therapy) as well as former study results for MOR00208 were used to justify assumptions on response rates ([Witzig et al., 2011](#); [Wang et al., 2013](#)).

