Statistical Methods and Data Analysis	The primary purpose of this study is to evaluate the clinical efficacy of oral LEN combined with MOR00208 administered by IV infusion in patients with R-R DLBCL. No formal statistical hypothesis testing will be performed. For the sample size determination it is assumed that the combination treatment could improve the ORR from a value of 20% (corresponding to monotherapy) to one of 35% which is achievable under combination treatment. Sample size estimation using a one-sample exact binomial test with a two-sided significance level of 5% and a power of 85% delivers a

	
sample size of 73 patients. According to this scenario an observed ORR of 32% would lead to a statistically significant study outcome. Allowing for a drop-out rate of 10% the total required sample size comes to approximately 80 patients.
 
All data will be summarised using appropriate statistics (counts/percentages for discrete variables, mean, median, standard deviation, minimum, maximum, number of valid observations for continuous variables) for tabulation purposes. For specific variables, p-values and 95% confidence limits will be presented.
 
Overall baseline and demographic data will be summarised using appropriate statistics. Patient disposition and status at the end of the study will be tabulated presenting the number of patients and frequencies. General medical history and history of DLBCL, including prior cancer therapies, will be tabulated using coding systems (e.g., MedDRA, WHO-DDE), where appropriate.

	
PRIMARY OBJECTIVE:

	
Primary efficacy endpoint: Objective response rate (ORR)
 
The ORR will be the percentage of patients who have met the ORR definition up until progression based on the central (independent) radiological and clinical evaluations. The denominator for calculating the rate will be based upon the total number of patients in the full analysis set (FAS) population. As a sensitivity analysis, patients without any post-baseline assessment of response will be included in the denominator for ORR calculation. Number of patients being a responder and the respective rates, as well as 95% confidence limits, will be presented.

	
SECONDARY OBJECTIVES:

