1.3.1 LEN as a Single Agent in Relapsed DLBCL

It has been demonstrated that LEN has single-agent activity in R-R DLBCL. [Wiernik et al. \(2008\)](#) evaluated the safety and efficacy of 25 mg LEN administered orally, daily, for 52 weeks, until disease progression or intolerance as monotherapy in patients with R-R aggressive NHL. The primary endpoint was ORR; secondary endpoints included duration of response (DoR), progression-free survival (PFS), and safety. Forty-nine patients with a median age of 65 years received LEN in this study. The most common histology was DLBCL, established in 53% of patients, and patients had received a median of four prior treatment regimens for NHL. The ORR was 35% including a 12% complete response (CR)/unconfirmed CR rate. Of patients with stable disease (SD) or partial response (PR) at first assessment, 25% improved with continued treatment. Estimated median DoR was 6.2 months, and median PFS was 4.0 months. The most common grade 4 adverse events (AEs) were neutropenia (8.2%) and thrombocytopenia (8.2%).

Similarly, in a phase II study of LEN in patients with R-R DLBCL, MCL, follicular grade 3 lymphoma (FL-3), or transformed lymphoma (TL) patients received oral LEN 25 mg on days 1–21 every 28 days as tolerated or until progression ([Witzig et al., 2011](#)). Two hundred and seventeen patients were enrolled and received LEN. The ORR was 35% (77/217), with 13% (29/217) of patients achieving CRs, 22% (48/217) PRs, and 21% (45/217) with SD. The ORR for DLBCL was 28% (30/108). Median PFS for all 217 patients was 3.7 months. For 77 responders, the median DoR was 10.6 months. The most common AE was myelosuppression, with grade 4 neutropenia and thrombocytopenia in 17% and 6% of patients, respectively.

[Zinzani et al. \(2014\)](#) have shown in a retrospective, multicentre study that LEN monotherapy is effective and safe for heavily pretreated patients with R-R NHL. The ORR in 64 evaluable patients was 42.2% and was similar among patients receiving 10, 15 or 25 mg/day LEN. ORR in patients with MCL, DLBCL and FL were 45.5%, 42.1% and 20%, respectively. Mean DoR in patients receiving any LEN dose was 10.5 months; 1-year PFS and OS rates were 50.3% and 82.6%, respectively.

Additionally it has been shown that single agent LEN was active in heavily pretreated patients with aggressive, R-R NHL subsequent to a prior ASCT ([Vose et al., 2013](#)).

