5.3 Determination of sample size

Approximately 80 patients with R-R DLBCL who meet all of the inclusion criteria and have none of the exclusion criteria will be enrolled into the study. The study will be performed with an interim stop for the evaluation of the safety of the LEN dosage. No adjustment of sample size or adaptation of efficacy evaluations will be made at this point. As the primary purpose of this study is to evaluate the clinical efficacy of 25 mg daily oral LEN combined with 12 mg/kg MOR00208 administered by IV infusion in patients with R-R DLBCL, no formal statistical hypothesis testing will be performed.

**STATISTICAL ANALYSIS PLAN**MorphoSys AG
MOR208C203

For the determination of a suitable sample size, it is assumed that the combination treatment could improve the ORR of LEN from a value of 20% (under monotherapy) to 35% (under combination therapy). Applying an exact binomial test with a two-sided significance level of 5% and a power of 85% the estimated sample size is 73 patients (calculation performed by nQuery Advisor® 7.0). According to this scenario an observed ORR of 32% would lead to the conclusion that the outcome is statistically superior to outcomes observed previously for the monotherapy. Assuming a drop-out rate of 10%, a total sample size of about 80 patients is estimated.

The sample size determination has been conducted using various possible monotherapy and combination effect ORR rates and various power assumptions. Literature evaluation of study results concerning the ORR rates of LEN or comparable products (as mono- or combination therapy) as well as study results for MOR00208 ongoing studies were used to justify assumptions on response rates (Witzig et al., 2011; Wang et al., 2013).

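### On the Clopper-Pearson interval the SAP will report, 73 patients give 77% power rather than the stated 85%; separately, SAP 5.3 claims superiority over earlier lenalidomide results that a 32% ORR would not show

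*Protocol*

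**What the plan says.** Protocol 10.8 assumes the combination raises the ORR from 20% to 35% and states: "Applying an exact binomial test with a two-sided significance level of 5% and a power of 85% the estimated sample size is 73 patients". It continues: "According to this scenario an observed ORR of 32% would lead to a statistically significant study outcome", and then: "Assuming a drop-out rate of 10%, a total sample size of about 80 patients is estimated". The synopsis gives the same figures.

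SAP 5.3 repeats the calculation with two changes. It identifies the 20% as lenalidomide's own rate ("improve the ORR of LEN from a value of 20% (under monotherapy) to 35"%), and it rewrites the sentence on the threshold: "According to this scenario an observed ORR of 32% would lead to the conclusion that the outcome is statistically superior to outcomes observed previously". The earlier outcomes it means are those on monotherapy. The same section says "no formal statistical hypothesis testing will be performed".

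SAP 9.2 reports the ORR on the FAS with a 95% Clopper-Pearson interval and counts patients without a post-baseline assessment as non-responders.

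Protocol 1.3.1 summarises earlier lenalidomide monotherapy. From the phase II study that Protocol 10.8 and SAP 5.3 also cite for their response-rate assumptions, it reports: "The ORR for DLBCL was 28% (30/108"). From a retrospective multicentre study it gives 42.1% in DLBCL, without the DLBCL denominator.

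**The concern.** There are two separate points.

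**Power.** Exact two-sided binomial tests come in more than one form, and they can differ by one responder at the cut-off. The documents do not say which form produced 73 and 85%. The only exact method the SAP specifies for the result is the Clopper-Pearson interval, and with no test planned that interval is how the trial will be read against 20%. If 85% belongs to a different rule, the stated power overstates the chance that the reported interval will exclude 20%.

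**Superiority wording.** The calculation compares the trial with an assumed constant of 20%. SAP 5.3 turns this into a comparison with results actually observed on lenalidomide alone. The DLBCL results the protocol reports are higher than 20%. In a single-arm trial such a sentence, written in advance, can pass into the study report as a conclusion.

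**Working it through.** **Inputs.** Null ORR 20%, target 35%, two-sided 5%, 85% power, n = 73, threshold 32%, 10% drop-out, about 80 enrolled (Protocol 10.8, SAP 5.3). Clopper-Pearson interval, with unassessed patients as non-responders (SAP 9.2). Earlier lenalidomide ORR in DLBCL 30/108 (Protocol 1.3.1).

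**1. Reproducing 73 and 85%.** The normal approximation gives

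n = [(1.960·√(0.20·0.80) + 1.036·√(0.35·0.65)) / 0.15]² = [(0.784 + 0.494) / 0.15]² = 72.6, rounded up to 73, with 85.2% power at 73.

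This matches the stated pair. That it was the source is an inference; the documents name only the software and an exact test.

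**2. Exact rules at n = 73.** X is the number of responders.

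| Cut-off | Observed ORR | P(X ≥ cut-off) at 20% | Power at 35% | 95% Clopper-Pearson interval at the cut-off |
|---|---|---|---|---|
| 22 | 30.1% | 0.0257 | 84.0% | 19.94% to 42.0% |
| 23 | 31.5% | 0.0135 | 77.1% | 21.1% to 43.4% |

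Excluding 20% with a Clopper-Pearson interval requires an upper-tail probability of at most 0.025. A count of 22 misses this narrowly, so the cut-off is 23 and the power is 77.1%. The minimum-likelihood form of the exact test does reject at 22 (p = 0.039), with 84.0% power; it first reaches 85% at n = 74 (85.9%).

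The documents' threshold of 32% corresponds to 23/73 = 31.5%. That result is significant against 20% under each convention tried: two-sided p is 0.027 (doubled one-sided), 0.020 (mid-p) and 0.019 (minimum-likelihood). The 32% sentence is therefore sound. But the power at that cut-off is 77%. Power near 85% from 73 patients needs a cut-off near 30%.

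**3. n = 80.** The Clopper-Pearson cut-off is 24/80 (30.0%; interval 20.3% to 41.3%), with P(X ≥ 24) = 0.0217 at 20% and power 85.5% at 35%. No n from 73 to 79 reaches 85% on this rule.

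That 85.5% requires 35% to hold across all 80. Suppose instead, as an assumption, that 35% holds only among evaluable patients and the others count as non-responders. Power at 24/80 is then:

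- 7 of 80 not evaluable: 68.9% with a fixed number of non-responders, or 68.4% using an overall rate of 0.35 × 73/80 = 31.9%.
- 8 of 80 (10%) not evaluable: 65.9% with a fixed number, or 65.4% using an overall rate of 0.35 × 0.90 = 31.5%.

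**4. The superiority wording.** The intervals at about 32% are 21.1% to 43.4% (23/73) and 22.4% to 43.9% (26/80). Both exclude 20% and both include 28%. Taking 28% as a fixed reference, the doubled one-sided p-value is 0.58 at 23/73 and 0.44 at 26/80. The 42.1% from the retrospective study is above the 32% estimate itself.

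**The case against.** The strongest reply is that nothing was miscalculated. The pair 73 and 85% follows from the normal approximation, and the minimum-likelihood exact test comes within a point. Sizing with one method and reporting a Clopper-Pearson interval descriptively is common practice, and no document makes exclusion of 20% by that interval a success criterion. The FAS should also be close to 80 rather than 73, because it takes everyone who received both drugs and keeps unassessed patients. At 80 the Clopper-Pearson power is 85.5%, although it moves unevenly with n: 83.6% at 79 and 81.4% at 81. The figures of 65% to 69% rest on an assumption, and a patient who drops out after responding still counts as a responder.

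Much of this stands. The point is not that 73 is an arithmetic error, and at about 80 patients the shortfall largely disappears if 35% applies to all of them. But the documents present 80 as 73 plus a drop-out allowance and attach the 85% to 73. They call the test exact, and no exact form tried gives 85% at 73. Their 32% goes with 77%.

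On the wording, SAP 5.3 does limit its sentence to the scenario just described. In addition, 30/108 is itself imprecise (95% interval 19.6% to 37.2%, which includes 20%), and the 42.1% comes from a retrospective study using several doses. These are reasons not to treat 28% or 42.1% as a benchmark. They do not support a claim of statistical superiority over results already observed, which the calculation never tests.

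**Conclusion.** Both points hold.

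On the interval SAP 9.2 will report, 73 patients give 77.1% power at a 35% ORR, 8 points below the stated 85%. At 80 analysed patients it is 85.5%, on the condition that 35% is the true rate among all 80. The documents do not say whether it is.

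SAP 5.3 overstates what a 32% result would show. It would exclude the assumed 20%. It would not exclude the 28% from the lenalidomide study cited to justify the assumptions.

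The consequences are limited to the design justification and the interpretation. No formal test depends on these figures, and the 32% threshold is valid against 20%.

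**What to change.** In Protocol 10.8, the synopsis and SAP 5.3 (or, if the protocol will not be amended again, in SAP 5.3 and the study report):

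- Name the exact method and restate the power on it: 77% at 73 patients (23/73 or more), and about 85% at 80 analysed patients (24/80 or more) if the true ORR among all 80 is 35%.
- Ask the sponsor whether the 35% refers to all FAS patients or only to evaluable patients, and record the answer.

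In SAP 5.3, replace the claim of superiority over earlier monotherapy outcomes with a statement that the lower 95% confidence limit would exceed 20%. Add that a 32% result does not exclude the 28% in Protocol 1.3.1.

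The cost is wording in three places and one question to the sponsor. Enrolment, analysis and threshold do not change. The price is a less favourable stated power and a softer claim in SAP 5.3.
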